- Within-host variation in influenza strains between the first and the third viral swab
- Cost effectiveness, assessed using health resource utilization (visit to clinic, hospital, pharmacy, emergency department) and school and work absenteeism
- Proportion with antiviral resistance, assessed by genetic sequencing of influenza strains from the drug eligible and drug ineligible study participants

Hypothesis

Primary hypothesis:

- A home-based approach to influenza infection control will result in a large percentage of drug eligible individuals diagnosed with influenza initiating antiviral therapy within 48 hours of symptom onset.

Secondary hypotheses:

- Home-based approach to influenza infection control and rapid delivery of antiviral therapy will decrease symptom severity in the drug eligible individuals diagnosed with influenza that administer antiviral therapy within 48 hours of symptom onset compared to drug eligible, influenza-infected individuals that administer antiviral therapy greater than 48 hours after symptom onset.
- Home-based approach to influenza infection control and rapid delivery of antiviral therapy will decrease the duration of viral RNA detection in the drug eligible, influenza-infected individuals that administer antiviral therapy within 48 hours of symptom onset compared to drug eligible, influenza-infected individuals that administer antiviral therapy greater than 48 hours after symptom onset.

IV. Study Population

The study will be conducted in households with at least 3 members, where at least 2 of these members must be eligible to receive BXM, in the Seattle area. Participants aged 12 years or older, weighing at least 40 kg, will be drug eligible. Participants of any age that reside in the same household as the case at least 4 days per calendar week will be drug ineligible study participants. Drug eligible study participants will receive baloxavir intervention when appropriate,

and all drug eligible and drug ineligible participants will receive a 7-day follow-up from the study team per illness episode.

Study size

The study is being conducted in the Seattle, WA area over one influenza season. The goal is to enroll 250 households, with enrollment occurring prior to and during the annual influenza season.

Household enrollment criteria

The household must meet all the following enrollment criteria:

Household inclusion criteria

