4. Additionally, one week later, the ill individual will complete day 7 of the illness questionnaire, which will ask information about respiratory and systemic symptoms, recent travel history, and absenteeism in 7 calendar days following the onset of a cough in the ill participant.

Immediately following the onset of an acute cough or 2 or more respiratory symptoms in a drug eligible participant, the following procedures will occur:

1. The person will self-test for influenza using the prepositioned home-testing kit as long as the following criteria are met:
 - Symptom duration <48 hours
 - Cough present or 2 or more respiratory symptoms present
 - i. Qualification for receipt of study drug will be determined based on a review of medical information with the tele-health provider. If the individual meets the required criteria (symptom duration <48 hours) and is diagnosed with probable influenza by a healthcare provider, this will trigger subsequent delivery of the intervention, if deemed appropriate.
2. Next, the ill individual will collect a nasal swab sample via self-swab or parent/legal guardian-swab as soon as possible. These specimens will then be packaged and shipping back to the laboratory via a delivery service for testing and further characterization. Additionally, the ill individual will complete day 0 of illness questionnaire in REDCap, which will ask information about respiratory and systemic symptoms, recent travel history, and absenteeism.
3. Concurrently, the participant will connect with a provider via the tele-health app previously downloaded on their smartphone. The provider will review the participant's symptoms and determine whether influenza infection is likely to be the underlying cause of the symptoms. If probable influenza is diagnosed, the tele-health provider will prescribe a weight-based dose of BXM. If antiviral treatment is not deemed appropriate by the tele-health provider, this information will be documented in the post-visit Care Plan for the study participant and subsequently shared with the study team.
4. Next, the study pharmacy will be notified that the participant is being prescribed BXM.

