Data Items	Enrollment	Weekly during Influenza Season	Monthly during Influenza Season	Influenza not diagnosed, drug eligible group	Influenza diagnosed, drug eligible group	Sick, drug ineligible group
Informed consent	X					
Baseline health and demographic data collected	X					
Baseline nasal swab collection	X					
Self-monitor cough or 2 or more respiratory symptoms		X				
Report changes in household structure or influenza vaccine status			X			
Nasal swab collection (Study day 0)				X	X	X
Nasal swab collection (Study day 2-3)					X	
Nasal swab collection (Study day 5-7)					X	
Illness questionnaire (Study day 0, Study day 7)				X	X	X

Record timing of drug receipt					X	
Standard questionnaire for AEs and SEAs (48 hours , 7 & 14 days post-treatment)					X	

Medication management

Baloxavir (BXM)

Drug eligible, influenza-infected study participants will receive a one-time oral dose of baloxavir (Xofluza) based on weight. For individuals weighing 80kg or more, they will receive 80mg of BXM. For individuals weighing 40-80kg, they will receive 40mg of BXM (See Table 2). The drug will be delivered to the individual's home within 2-6 hours of an influenza diagnosis. The case will be instructed to take the medication immediately on receipt and record the time of ingestion using the REDCap app or by text message. The description of the antiviral from the product monograph is as follows:

XOFLUZA™ is a polymerase acidic (PA) endonuclease inhibitor indicated for the treatment of acute uncomplicated influenza in patients 12 years of age and older who have been symptomatic for no more than 48 hours.

Limitations of Use: Influenza viruses change over time, and factors such as the virus type or subtype, emergence of resistance, or changes in viral virulence could diminish the clinical benefit of antiviral drugs. Consider available information on drug susceptibility patterns for circulating influenza virus strains when deciding whether to use XOFLUZA.

Medication storage and packing

BXM blister packs will be provided to the study team prior to the start of the influenza season by the drug manufacturer or purchased from the manufacturer. According to the manufacturer, baloxavir should be stored in its blister package at 20°C to 25°C (68°F to 77°F); excursions permitted to 15°C to 30°C (59°F to 86°F). Additional storage recommendations are provided below.

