- 20 mg white to light yellow, oblong shaped film-coated tablets debossed with “Ø772” on one side and “20” on the other side available as:
 - 2 x 20 mg tablets per blister card in secondary packaging: NDC 50242-828-02
 - 4 x 20 mg tablets per blister card in secondary packaging: NDC 50242-828-02
- 40 mg white to light yellow, oblong shaped film-cated tablets debossed with “BXM40” on one side available as:
 - 1 x 40 mg tablet per blister card in secondary package: NDC 50242-860-01
 - 2 x 40 mg tablets per blister card in secondary packaging: NDC 50242-860-02

Upon receiving a prescription for antiviral medication from a tele-health provider, a study pharmacist will pull the blister pack or packs from the correct weight bin, which will be organized prior to the start of the influenza season, and dispense the medication.

Following the packaging and labeling of the intervention, an informational hand out about the study drug will be included in this packaging along with the contact information for a licensed medical professional associated with the study who is available to answer any follow-up questions the participant may have regarding the intervention. Furthermore, the drug eligible participant will also be able to direct drug related questions to a 98point provider via the tele-health app.

Medication delivery and counseling

After the intervention is dispensed, the rapid delivery service will be notified that the study drug is available for delivery. Next, the rapid delivery service will pick up the intervention and deliver the package to the household of the case within 2-6 hours of an influenza diagnosis . Once the medication leaves the storage facility, delivery tracking will be performed by a member of the study staff and a log recording successful medication delivery will be kept as additional quality assurance measure.

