If the adverse event is considered by the medical expert team to be minor in severity, it will be logged in the centralized data capture system and a summary of such events will be reported to the DSMB. If the severity of the adverse event is considered to be moderate or severe by Principal and Co-Principal Investigators, it should be reported to the safety officer (DSMB) and the cognizant IRB immediately. All study-related SAEs will be reported to the IRB within 14 days.

The following are a list of anticipated and unanticipated adverse events we expect to be attributable to the study procedures or the intervention:

Anticipated Events: Mild-moderate systemic reactions, these include diarrhea, bronchitis, nausea, nasopharyngitis, and headache.

Unanticipated Events: By definition these are unexpected in terms of their nature, (see above for anticipated events) severity, and frequency, especially if they indicate that there may be greater risk of harm than previously recognized.

X. Definitions

Acute Respiratory Illness/infection (ARI): We will use the CDC definition of ARI that includes disease that typically involves the airways within the nose and throat and may or may not include fever. ARI is generally defined by the presence of two or more symptoms such as fever, cough, runny nose or nasal congestion, or sore throat. ARI is more sensitive (broader) than ILI to describe illness consistent with influenza because fever/feverishness are not required.

Drug eligible, influenza-infected study participant: A drug eligible study participant in the household that is diagnosed with influenza from a 98point6 provider based on a clinical review of the sick participant's symptoms.

Drug ineligible participant: A study participant in the household that is not able to receive BXM.

Influenza-like Illness in Adults and Adolescents (ILI): We will use the CDC definition of ILI that requires reported or measured fever ($>37.8^{\circ}\text{C}$) plus either cough or sore throat on one or more days preceding consultation with a tele-health physician.

Laboratory-confirmed influenza infection: We will use the CDC definition that is an individual who tests positive for influenza via an approved laboratory test, which will be the multiplex PCR (Cepheid) in this study.

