For the secondary endpoints of symptom duration and severity, drug eligible and drug ineligible participants will be analyzed separately. Symptom severity will be measured on a 4-point scale (0 = no symptoms, 1 = mild, 2 = moderate, 3 = severe) for each influenza-associated symptom the participant reports experiencing. Influenza-associated symptoms the participant does not report as experiencing will be coded as 0. An additional analysis will be conducted comparing secondary endpoints for drug eligible, influenza-infected study participants that received and initiated treatment within 48 hours of symptom onset and those that initiated treatment later than 48 hours. Kaplan-Meier curves will be used to present and analyze time to resolution of symptoms, defined as the time when the influenza-positive participant reports experiencing no respiratory or systemic symptoms. For study participants who received BXM, a Cox proportional hazards model will be used to calculate the hazard ratio, 95% confidence interval, and p-value for symptom duration by group (therapy within 48 hours of symptom onset, and therapy after 48 hours of symptom onset). The analysis of drug ineligible study participants will use a similar approach but will cluster by household and use a robust variance for computing confidence intervals and p-values. For BXM recipients, symptom severity will be compared between groups (therapy within 48 hours of symptom onset, and therapy after 48 hours of symptom onset) using proportions for categorical measures of severity and Pearson's chi-square test, as well as using ordinal regression. As above, the analysis using ordinal regression of drug ineligible study participants will cluster by household and use a robust variance for computing confidence intervals and p-values.

For the secondary endpoints of maximum viral titer and duration of viral RNA detection, we will use t-tests or nonparametric alternatives and linear regression to assess maximum viral titer and Kaplan-Meier curves and Cox proportional hazards models to assess duration of viral RNA detection.

Interim Analysis

This study is being conducted over the course of one influenza season. Therefore, an interim analysis will not be performed.

Antiviral resistance analysis

The secondary outcome data regarding emergence of BXM resistance will be reviewed at the end of the influenza season via genome sequencing of the viral RNA.

Health economic analysis

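### The self-test and the baloxavir trigger are both limited to symptoms under 48 hours, so the after-48-hours comparator is unplanned and late presenters drop out of the primary denominator

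*Protocol*

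**What the plan says.** **Trigger and self-test.** For drug-eligible participants, Protocol V (Onset of Symptoms) states: "The person will self-test for influenza using the prepositioned home-testing kit as long as the following criteria are met", and the first criterion listed is symptom duration under 48 hours. On the drug it says: "If the individual meets the required criteria (symptom duration <48 hours) and is diagnosed with probable influenza by a healthcare provider, this will trigger" delivery, if deemed appropriate. The product description under Medication management covers patients "who have been symptomatic for no more than 48 hours". The courier is to "deliver the package to the household of the case within 2-6 hours of an influenza diagnosis", and the participant is told to take the dose on receipt.

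**Late group.** Both secondary hypotheses in Protocol III set treatment within 48 hours "compared to drug eligible, influenza-infected individuals that administer antiviral therapy greater than 48 hours after symptom onset". Protocol XI repeats the contrast with a Cox model, a chi-square test and ordinal regression; the Cox model is to give a hazard ratio and "p-value for symptom duration by group (therapy within 48 hours of symptom onset, and therapy after 48 hours of symptom onset"). Its health economic analysis builds an incremental cost-effectiveness ratio on the same split. Protocol X defines the influenza-infected, drug-eligible participant as one "diagnosed with influenza from a 98point6 provider based on a clinical review", so laboratory confirmation is not required for this comparison.

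**Primary denominator.** Protocol III (Primary Outcome Measures) counts only drug-eligible people who are both self-test positive and laboratory-confirmed.

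**SAP sensitivity analysis.** The question it poses concerns time of testing. The details under it re-run the model on people treated within 24, 48 and 72 hours. The SAP's outcome definition makes treatment within 48 hours a success, and later or no treatment a failure.

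**The concern.** Three analyses depend on people whom the procedures largely screen out.

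- The early/late contrast supports two hypotheses and the cost-effectiveness ratio. If almost nobody is treated late, the hazard ratio, p-values and ratio have almost no comparator. Those who are in the late group are there because of delay.
- The primary percentage is meant to show how often the home strategy achieves treatment within 48 hours. Presenting too late is one way the strategy can fail. A denominator that needs a self-test allowed only before 48 hours removes that failure and can flatter the result.
- A sensitivity analysis on subsets defined by the outcome itself cannot test robustness.

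**Working it through.** **1. The plan's own figures.** 250 × 25% = 62.5, rounded to 63 confirmed infections. The half-width is 1.96 × 0.5/√63 = 0.1235, which matches the stated 0.12 after rounding. The documents give no size for the late group.

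**2. Size of the late group (illustration).** Assumed inputs: 63 recipients, borrowed from the expected confirmed infections; the distribution of symptom duration at the check; and the lag L from check to dose. Only the 2–6 h from diagnosis to delivery is in the Protocol. With durations uniform over 0–48 h, the late share is f = L/48. With an exponential of mean m truncated at 48 h, f = [exp(−(48−L)/m) − exp(−48/m)] / [1 − exp(−48/m)]. Expected late starters are 63 × f:

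| Lag | Uniform | Exponential, m = 24 h | Exponential, m = 12 h |
|---|---|---|---|
| 2 h | 2.6 | 0.9 | 0.2 |
| 6 h | 7.9 | 2.8 | 0.8 |
| 12 h | 15.8 | 6.4 | 2.0 |
| 24 h | 31.5 | 16.9 | 7.5 |

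The chance of an empty late group is (1−f)^63. At a 2 h lag it is 7%, 42% and 81% across the three columns; at 6 h it is under 1%, 6% and 46%.

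The number of recipients matters as much. Up to one per household is possible, because diagnosis is clinical and each household has one course. At 250 recipients and a 6 h lag, the uniform case gives 250 × 6/48 = 31 and the m = 12 h case gives 0.76 × 250/63 = 3.

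**3. What such a group can show.** If every recipient's symptom resolution is observed, the hazard ratio detectable with 80% power at two-sided 5% is exp(2.80/√(n f (1−f))). Under uniform durations:

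- n = 63, f = 2/48: exp(2.80/√2.52) = 5.8
- n = 63, f = 6/48: exp(2.80/√6.89) = 2.9
- n = 250, f = 6/48: exp(2.80/√27.3) = 1.7

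**4. Primary denominator.** The primary outcome needs a positive self-test, and Onset of Symptoms permits the test only before 48 hours. Read together, a person presenting at or after 48 hours cannot enter the denominator. Other sections imply other denominators:

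- Protocol II and the Data collection part of Protocol V describe the self-test without a 48 h limit.
- Protocol XI refers to people with an influenza diagnosis, and in its precision formula to people who test positive.
- SAP B6 divides by all influenza-free participants at baseline.

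For the size of the effect, assume a reported 85% and a share q of PCR-confirmed drug-eligible illnesses presenting late. If self-test false negatives are treated in time as often as true positives, the proportion over all such illnesses is 0.85 × (1−q):

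- q = 10%: 0.765
- q = 20%: 0.68
- q = 40%: 0.51

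The shift exceeds the plan's ±0.12 once q passes 0.12/0.85 = 14%. If no false negative is treated in time and sensitivity is an assumed 75%, the 20% case becomes 0.85 × 0.80 × 0.75 = 0.51.

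**5. SAP sensitivity analysis.** Take the subsets by treatment time, as its details say, with the SAP's success/failure outcome. Everyone treated within 24 or 48 hours is a success by definition, so the outcome does not vary and no risk ratio can be estimated. The 72 h subset adds people treated between 48 and 72 hours as failures but omits everyone never treated, whom the SAP also calls failures.

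**The case against.** The strongest reply is that this is a feasibility pilot, that Protocol XI calls the early/late comparison an additional analysis, and that no power is claimed for it. That is fair, and it supports labelling the contrast descriptive. It does not explain why hazard ratios, p-values and directional hypotheses are attached to it.

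Several stronger readings are tempting, and the documents do not support them.

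- A reader might infer that the late group must be a handful of people, or empty. The 0.2–8 range is one scenario. The Protocol sets no limit on the gap between self-test and consultation, and the 2–6 h runs only from diagnosis to delivery. Study design, step 3 of the drug-eligible procedure and Data collection describe prescribing on provider judgement without repeating the 48 h limit. Deviations or misreported onset could also add late starters.
- A reader might infer that no other endpoint covers late presenters. Two secondary endpoints, delivery within 48 hours and self-reported administration within 48 hours, have open denominators and could include them.
- A reader might infer that the SAP sensitivity analysis fails on every reading. If subsets are formed by testing time, or if the outcome is influenza incidence as its question suggests, the fits could run. The failure is specific to treatment-time subsets with the success/failure outcome.

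**Conclusion.** The inconsistency stands, and it should be resolved before analysis. It follows from the text that the within-protocol route to the late group is delay after the check, that its size is unplanned, and that the Protocol III primary denominator read with Onset of Symptoms excludes late presenters. That treatment-time subsets at 24 and 48 hours contain only successes follows from the SAP's definitions alone.

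The sizes are illustrations. The late-group range rests on assumed recipients, durations and lags. The fall from 85% to 68% rests on an assumed reported value, an assumed 20% late share and equal treatment of self-test false negatives; it would be larger if they are treated less often. The documents show that the primary percentage can overstate performance, but they do not say by how much.

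**What to change.** Changes to analysis wording only:

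1. Reconcile Protocol II, III, V (Onset of Symptoms and Data collection) and XI with SAP B6 so that there is one primary denominator. Beside it, report the number treated within 48 hours of onset divided by all PCR-confirmed illnesses in drug-eligible participants, whatever the presentation time. Late or untested illnesses that have a swab count as failures if not treated within 48 hours. Show illnesses in households that have already used their baloxavir course in a separate row. The procedure says "the ill individual will collect a nasal swab sample via self-swab or parent/legal guardian-swab as soon as possible", with no 48 h limit of its own, so no new collection is needed.
2. Replace the SAP's treatment-time subsets with three outcomes, treated within 24, 48 and 72 hours, each analysed on the full denominator.
3. Label the within/after 48 h contrasts and the cost-effectiveness ratio descriptive, and show the group sizes.

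The sections on the under-48-hours trigger and on the after-48-hours group must also be reconciled with each other; no clinical rule is proposed here.

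The cost is an edit to both documents and one extra proportion. Formal inference on the two-group contrast is lost, and the added proportion will look less favourable than the primary one.

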Person-to-person transmission: We will use the CDC definition for influenza transmission that refers to the ability of an influenza virus to spread from one person to another, most commonly through large or small droplets containing influenza virus that are expelled when a sick person is coughing or sneezing.

XI. Statistical Analyses

The primary objective is to precisely estimate the proportion of drug eligible individuals with an influenza diagnosis who initiate treatment within 48 hours. We define precision in terms of the width of a 95% confidence interval. The width of a 95% CI will be less than or equal to $\pm 1.96 \cdot 0.5/\sqrt{n}$ where n is the number of individuals who test positive for flu. With 250 households participating and an attack rate of 25% we expect 63 individuals with confirmed influenza infection. This will give a 95% CI for the proportion initiating treatment of ± 0.12 or less.

The proportion of drug eligible individuals receiving the drug and initiating treatment within 48 hours of symptom onset using home-based self-test and delivery methods will be estimated. Binomial regression with log link will be used to calculate the relative risk of receiving and initiating treatment within 48 hours by demographic and clinical factors, including age, sex, race/ethnicity, symptom types, symptom severity, and duration of symptoms. The RR, 95% confidence intervals and p-values will be reported.

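### The Pearson chi-square test of symptom severity by treatment time has no small-sample provision; an exact rank test would hold its level whatever the size of the late group

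*Protocol*

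**What the plan says.** Protocol section XI scores each symptom as follows: "Symptom severity will be measured on a 4-point scale (0 = no symptoms, 1 = mild, 2 = moderate, 3 = severe". It adds: "Influenza-associated symptoms the participant does not report as experiencing will be coded as 0". Those given BXM are then split by when they started it: "symptom severity will be compared between groups (therapy within 48 hours of symptom onset, and therapy after 48 hours of symptom onset". The methods are proportions with Pearson's "chi-square test, as well as using ordinal regression". The section gives no exact version, no rule for sparse cells, no collapsing of categories, and no statement of which of the two analyses governs.

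The SAP lists symptom severity as a secondary objective (section A, S3) but names no test for it, so protocol section XI is the only specification. The comparison serves a stated secondary hypothesis (protocol section III, Hypothesis) that early treatment lowers severity.

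Two other parts of the protocol bear on group size. Under Onset of Symptoms, delivery of drug is triggered on this condition: "If the individual meets the required criteria (symptom duration <48 hours", plus a provider's diagnosis of probable influenza. Section XI gives the planning count: "With 250 households participating and an attack rate of 25% we expect 63 individuals with confirmed influenza infection".

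**The concern.** Pearson's p-value rests on a large-sample distribution that becomes unreliable when expected counts are small. Here the late row is likely to be short. A participant must be under 48 hours from onset to qualify, and delivery is planned within 2–6 hours of diagnosis. If that target is met and the drug is taken on receipt, only someone diagnosed after about hour 42 (48 − 6) can be treated late. The primary hypothesis also expects most people to start in time. So the better the strategy works, the sparser this comparison becomes.

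Coding unreported symptoms as 0 adds to the sparseness. The symptom table in section II includes items such as rash, ear pain or discharge, and diarrhea. If most participants do not have them, nearly everyone falls in category 0 and the other three columns are almost empty. A single late participant with an uncommon severe score can then produce a nominally significant difference.

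**Working it through.** **The plan's own figure.** 250 × 0.25 = 62.5, rounded to 63. The half-width is 1.96 × 0.5/√63 = 0.1235, which agrees after rounding with "This will give a 95% CI for the proportion initiating treatment of ± 0.12 or less". No size, power or expected count is given for the severity test.

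**Inputs.** From the documents: two groups and four score levels (section XI). Assumed: N = 63 recipients; 2 to 32 treated late; the symptom distributions shown below; all four levels in one table; nominal level 5%. The one-sided 0.05 in SAP section B6 is attached to the primary model, and no level is set for this comparison.

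**Expected counts.** Expected late cell = (number late) × (category share).
- The smallest of four shares is at most 1/4, so the smallest late cell is at most (number late)/4. This is below 5 whenever fewer than 20 are late.
- With 8 late, a cell reaches 5 only if its share is at least 5/8 = 62.5%. The other three cells then total at most 8 × 37.5% = 3. At least three of the four late cells are therefore below 5, whatever the symptom frequencies.

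**Actual size under no difference, N = 63.** Tables were enumerated in full given their margins and averaged over simulated margins. Empty columns were dropped and the degrees of freedom adjusted. Entries are the percentage rejected at nominal 5%; column headings give the shares scoring 0/1/2/3.

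| Late | Pearson, 25/25/25/25 | Pearson, 60/20/15/5 | Pearson, 80/10/7/3 | Pearson, 90/5/3/2 | Exact Wilcoxon, range over all four |
|---|---|---|---|---|---|
| 3 | 4.2 | 6.9 | 9.9 | 11.7 | 2.6–4.0 |
| 6 | 4.3 | 6.2 | 8.5 | 10.8 | 3.6–4.5 |
| 9 | 4.6 | 5.4 | 6.4 | 8.3 | 3.4–4.8 |
| 13 | 4.7 | 5.0 | 5.2 | 5.9 | 3.5–4.9 |
| 19 | 4.9 | 4.4 | 3.6 | 3.0 | 3.4–4.9 |

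Separate simulation gave 8.2–10.5% for 80/12/6/2 items and 5.8–7.9% for 60/25/10/5 items with 2–8 late. With 25–32 late, Pearson rejected 1.3–4.1% for the items concentrated at 0. With N = 100 or 150 and 5–10% late, items with at least 80% at 0 still gave 6.1–11.3%.

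**One table by hand.** Take 3 late of 63, with early scores 49/7/3/1 and late scores 2/0/0/1. The column totals are 51/7/3/2, so the expected late counts are 2.43, 0.33, 0.14 and 0.10. The late row contributes 0.08 + 0.33 + 0.14 + 8.60 = 9.15. The early row, with expected counts 20 times larger, contributes 9.15/20 = 0.46. The statistic is about 9.60 on 3 degrees of freedom, p = 0.022.

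By chance, at least one of the two severe scores falls among the three late people with probability 1 − (60 × 59)/(63 × 62) = 0.094. Every such table has a statistic at least this large, so the exact Pearson p-value is at least 0.094.

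For the exact Wilcoxon test, the midranks are 26, 55, 60 and 62.5. The late rank sum is 26 + 26 + 62.5 = 114.5 against an expected 3 × 32 = 96, a deviation of 18.5. Late sets at least as far from 96 are one severe score with two zeros, 2 × C(51,2) = 2,550, and two or more non-zero scores, C(12,2) × 51 + C(12,3) = 3,586. The p-value is (2,550 + 3,586)/C(63,3) = 6,136/39,711 = 0.155.

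**The case against.** The strongest reply is that the plan already has an ordered analysis. The sentence that names Pearson's test also names ordinal regression, on the same score and the same groups. A reader might infer that the plan ignores the ordering of the scale, or that it lacks power to detect a shift. Neither is supported. For an assumed large shift (35/35/20/10 early against 10/20/35/35 late, N = 63), simulation of a proportional-odds model with a likelihood-ratio test rejected 69% with 8 late and 51% with 5 late, against 55% and 41% for Pearson. The plan's own model is therefore not short of power relative to an exact rank test (64% and 47% in a separate simulation of the same shift).

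That reply does not make the Pearson p-value valid. Nor can the ordinal model always stand in for it. When every late participant scores 0, it has no finite estimate. With 80% of people at 0, the chance of this is about 0.8³ = 51%, 0.8⁵ = 33% and 0.8⁸ = 17% with 3, 5 and 8 late; simulation, counting either extreme category, gave 52%, 32% and 16%. The likelihood-ratio test's own size ranged from 2.3% to 8.3% in null settings with 3 to 19 late.

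Other limits stand in full. The documents give no late share and no symptom frequencies, and the direction of the error depends on both. Sixty-three is a count of confirmed infections, not of BXM recipients: drug-ineligible cases would lower it, and treatment on a clinical diagnosis could raise it. The protocol speaks only of categorical measures of severity, so a table with all four levels is a fair reading but not a stated one. The endpoint is secondary, in a feasibility pilot whose primary objective is estimation.

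**Conclusion.** The point holds as a minor correction. Pearson's test is specified without a small-sample provision in a comparison whose late group is small by design. Under the stated assumptions (N about 63, all four levels tabulated, about 2–9 late), it rejects roughly 6–10% at nominal 5% for symptoms that most participants score 0. The computed extremes reach 5.4% at 9 late for the least skewed of these items and nearly 12% at 3 late for the most skewed. At 13 late the excess is small (5–6%), and at 19 or more the test is conservative for such symptoms. Evenly spread symptoms show no inflation.

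A reader might conclude that all p-values for this secondary hypothesis are wrong. That goes too far, because the error is confined to particular splits and symptom frequencies that cannot be known in advance. That uncertainty is the reason to choose a test whose level does not depend on them.

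**What to change.** In protocol section XI, replace the Pearson p-value with a two-sided exact (permutation) Wilcoxon rank-sum test on the 0–3 score of each symptom. It holds its level at any split between early and late. Report the proportions in each category descriptively by group. Keep the planned ordinal regression for the effect estimate and interval where it can be fitted, and say that it will be reported as not estimable where it cannot. Carry the same sentence into the SAP, which has none.

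The cost is one sentence and a few lines of R, with no change to data collection. The downside is a slightly conservative p-value when ties are heavy or very few people are treated late (actual size about 2.5–5%). The change does not make a small late group informative: even for the large shift above, the exact test has about 47% power with 5 late.
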